8.5.2.2 Dose Response Analysis

The change from baseline LSMeans for the HRpQCT results for the Trabecular vBMD (radius) will further be analysed using the MCPMod methodology, using the following candidate models:

- EMax (ED₅₀ of 1.5 mg)
- Exponential ($\delta = 2$)
- Sigmoid EMax (ED50 of 1.5 mg and h=2.4)

Parameter estimates and predicted values for each dose will be calculated for all models. This analysis will be repeated for the bone strength on FEA for supportive evidence.

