The HRpQCT results will be log transformed and an ANCOVA model will be used to calculate Least Square Means (LSMeans) for the change from baseline, using baseline values as a covariate and treatment group and stratum as a factor. LSMeans for each treatment group will be calculated and tested against the null hypothesis of 0 in an a priori hierarchical approach, starting with the highest dose. Differences between LSMeans will also be displayed but will be analysed in an exploratory fashion only. The type I error rate will be 5% two-sided. P-values above 5% but below 10% (two-sided) will be considered as indicative for a trend.

The LSMeans will further be analysed using the MCPMod methodology, using the following candidate models:

- EMax (ED₅₀ of 1.5 mg)
- Exponential ($\delta = 2$)
- Sigmoid EMax model with parameters ED50 = 10 mg and h = 2.4

Parameter estimates and predicted values for each dose will be calculated for all models. These analyses will be done primarily on the trabecular vBMD (radius). It will be repeated for the bone strength on FEA for supportive evidence.

LSMeans and LSMean differences between treatment groups will be back-transformed to their original scale for descriptive purposes. After subtracting the geometric mean of the log baseline values, the back-transformed LSMeans will correspond to the percentage change from baseline,

while the back-transformed LSMeans differences will correspond to the ratio of percentage changes from baseline.

The remaining efficacy variables will be analysed according to their scale using general methods as described above.

Exploratory Analyses

Exploratory endpoint variables will be analysed according to their scale using general methods as described above.

Safety Analyses

Variables will be analysed according to their scale using general methods as described above, and results will be presented overall and by treatment group.

Follow-Up Period Analyses

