11.3.1. Efficacy Analyses

Analyses for the primary efficacy endpoints and selected secondary endpoints will be analysed on the FAS, mFAS, the Non-restricted FAS and the PP samples, while analyses for the remaining secondary efficacy endpoints will be analysed on the FAS sample only. The mFAS will be used for analysis of HRpQCT endpoints only. General methods as described above will be applied to the efficacy endpoints; specific analyses are described below.

Endpoint	Statistical Analysis Methods
Primary	
The HRpQCT results for the Trabecular vBMD (radius) will be log transformed and an ANCOVA model will be used to calculate Least Square Means (LSMeans) for the change from baseline, using baseline values as a covariate and treatment group and stratum as a factor. LSMeans for each treatment group will be calculated and tested against the null hypothesis of 0 in an a priori hierarchical approach, starting with the highest dose. Differences between LSMeans will also be displayed but will be analysed in an exploratory fashion only. The type I error rate will be 5% two-sided. P-values above 5% but below 10% (two-sided) will be considered as indicative for a trend.
 
For supportive evidence, this analysis will be repeated on the mFAS, Non-restricted FAS in both versions and the PP population. Further,

Endpoint	Statistical Analysis Methods
	
the following analyses will be performed, again on the FAS, mFAS, the Non-restricted FAS in both versions and the PP population:
 
The LSMeans will further be analysed using the MCPMod methodology, using the following candidate models:
 
 • EMax (ED₅₀ of 1.5 mg) • Exponential ($\delta = 2$) • Sigmoid EMax model with parameters ED₅₀ = 10 mg and h = 2.4 
Parameter estimates and predicted values for each dose will be calculated for all models.
 
These analyses will be done primarily on the trabecular vBMD (radius). It will be repeated for the bone strength on FEA for supportive evidence.
 
LSMeans and LSMeans differences between treatment groups will be back-transformed to their original scale for descriptive purposes. After subtracting the geometric mean of the log baseline values, the back-transformed LSMeans will correspond to the percentage change from baseline, while the back-transformed LSMeans differences will correspond to the ratio of percentage changes from baseline.

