1 INTRODUCTION

The purpose of this Statistical Analysis Plan (SAP) is to provide detailed descriptions of the statistical methods, data derivations and data displays for study protocol MBPS205 Amendment 5 “A Phase 2b, Multicentre, Multinational, Double-blind, Dose-finding Study, incorporating an open label substudy, in Adult Patients with Type I, III or IV Osteogenesis Imperfecta Treated with setrusumab (BPS804)” dated 12 December 2018. The table of contents and templates for the Tables, Figures and Listings (TFLs) will be produced in a separate document.

Any deviations from this SAP will be described and justified in the Clinical Study Report (CSR).

The preparation of this SAP has been based on International Conference on Harmonisation (ICH) E9¹.

All data analyses and generation of TFLs will be performed using SAS 9.4® or higher.

Note: This plan does not address the validation analyses to the HRpQCT measurements or the pharmacokinetic (PK) analyses. These analyses will be described in a separate analysis plan.

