5 SAMPLE SIZE AND POWER

The number of participants is based on power considerations for the trabecular vBMD (radius) derived from HRpQCT at Month 12. The primary analysis method for this endpoint will be on the change from baseline within each treatment group, so the primary hypothesis to be tested is

$$H_0: \mu_T \leq 0 \text{ vs. } H_1: \mu_T > 0$$

where μ_T denotes the change from baseline for each dose of Setrusumab. Under the assumptions of a maximum change from baseline of [REDACTED], a standard deviation at both timepoints of [REDACTED] and a correlation between both measurements of [REDACTED] a sample size of 25 patients per group yields approximately 80% power for a one-sided test with significance level 0.025, if the data are analysed on the log scale using a t-test.

For a change from baseline of [REDACTED], with standard deviation as above the one-sided test would have a probability of 80% to yield a p-value below 5%, being considered indicative of a trend.

Following a review of the trabecular vBMD (radius) derived from HRpQCT at Month 6 of those patients within the 20mg/kg Setrusumab open label treatment group, a change from baseline standard deviation of [REDACTED] was observed. This yields to a correlation between baseline and month 6 visits of [REDACTED] (much higher than the [REDACTED] that was originally assumed). If such a correlation is observed at month 12, given 25 subjects per arm, the one-sided test would have a probability of 80% to yield a p-value below 5% for a change in baseline of [REDACTED].

As a secondary analysis, the MCPMod approach will be applied to the data in order to assess a non-flat dose-response curve and to obtain information about the underlying dose-response curve. Due to the missing placebo group, the power of this approach depends heavily on the underlying dose-response curve.

The following candidate models will be used:

- EMax (ED50 of 1.5 mg)
- Exponential ($\delta = 2$)

Under the assumptions of each of the two candidate models being the true dose-response curve, and in addition an Sigmoid EMax model with parameters ED50 = 10 mg and $h = 2.4$, a contrast test at a one-sided significance level of 2.5% has the following power for each of the three models:

Model	EMax	Exponential	Sigmoid EMax
Power	13.7%	73.2%	60.7%

The total sample size required is therefore determined as 100:

- 25 participants on open-label setrusumab (20 mg/kg)

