9 CHANGES TO PLANNED ANALYSIS FROM PROTOCOL

Not applicable.

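### SAP 8.5.2.2 sets the Sigmoid EMax candidate for MCP-Mod at ED50 = 1.5 mg, where the protocol's analysis sections set it at 10 mg, so the two documents pre-specify different dose-response tests

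*SAP*

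**What the plan says.** SAP 8.5.2.2 names three MCP-Mod candidates: EMax, given as "EMax (ED₅₀ of 1.5 mg"), Exponential with delta = 2, and "Sigmoid EMax (ED50 of 1.5 mg and h=2.4").

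Protocol 11.3.1 names the same three, but the third is "Sigmoid EMax model with parameters ED₅₀ = 10 mg and h = 2.4". The Efficacy Analysis part of the protocol synopsis agrees with 11.3.1.

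The sample-size texts (protocol synopsis, protocol 11.1, SAP 5) list only EMax and Exponential as candidates. They bring in the sigmoid curve as an extra truth for the power table; in the SAP's words, "in addition an Sigmoid EMax model with parameters ED50 = 10 mg". The stated powers are 13.7% (EMax), 73.2% (Exponential) and 60.7% (Sigmoid EMax).

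SAP section 1 says that the plan covers "data derivations and data displays for study protocol MBPS205 Amendment 5", while the protocol supplied is Amendment 6. SAP section 9, on changes from the protocol, reads "Not applicable".

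**The concern.** In the testing step of MCP-Mod the guessed parameters are part of the test. They set each candidate's contrast weights, the correlations between contrasts and hence the multiplicity-adjusted critical value. A change in ED50 from 10 to 1.5 at fixed h is therefore a change of test.

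The analysis serves the first-listed secondary objective, the dose-response of Tr. vBMD, in a dose-finding trial, and it is repeated for bone strength on FEA. If the documents stay as they are, someone must choose between two written tests, possibly after seeing the data. The SAP's version also drops the only candidate with an intermediate shape and replaces it with a near-copy of EMax. The value 1.5 is the ED50 of the EMax candidate in the same list. That suggests a carry-over, though the documents do not say so.

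**Working it through.** **Inputs.** Doses 2, 8 and 20 mg/kg, 25 participants per blinded arm, no placebo, one-sided 2.5% (protocol 11.1, SAP 5). Residual df = 75 - 3 = 72. The ED50 values are written in mg and are read here as mg/kg. The planned effect and SD are redacted, so the effect at 20 mg/kg in SD units is an assumption: 0.60, 0.68 and 0.80.

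**Step 1: reproduce the stated powers.** Each true curve is scaled to reach the assumed effect at 20 mg/kg, and the maximum-contrast test uses the two candidates of the sample-size text (simulated critical value 2.22). At 0.68 SD the powers are 13.7%, 73.2% and 60.7% for EMax, Exponential and Sigmoid EMax with ED50 = 10. One assumed value matches all three stated figures. With ED50 = 1.5 as the true curve, the same calculation gives 11.4%. Reaching 60.7% with that curve would need about 1.89 SD, at which EMax power would be 70% and not 13.7%. The stated 60.7% therefore belongs to the 10 mg curve.

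**Step 2: curve values and shape.** Sigmoid: f(d) = d^h / (ED50^h + d^h). EMax: d / (ED50 + d). Exponential: exp(d/2) - 1. The last column is the position of the 8 mg/kg mean, (f(8) - f(2)) / (f(20) - f(2)).

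| Curve | f(2) | f(8) | f(20) | Position of 8 mg/kg |
|---|---|---|---|---|
| Exponential | 1.718 | 53.60 | 22025 | 0.2% |
| Sigmoid, ED50 10 | 0.0206 | 0.3692 | 0.8407 | 0.3486/0.8201 = 43% |
| EMax, ED50 1.5 | 0.5714 | 0.8421 | 0.9302 | 0.2707/0.3588 = 75% |
| Sigmoid, ED50 1.5 | 0.6661 | 0.9823 | 0.9980 | 0.3162/0.3319 = 95% |

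The protocol's sigmoid lies between Exponential and EMax. The SAP's lies beyond EMax.

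**Step 3: contrasts.** With equal arms the optimal contrast is f(d) minus its mean, scaled to unit length.

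- ED50 = 10: mean 0.4102, deviations (-0.3896, -0.0410, 0.4305), length 0.582, contrast (-0.669, -0.070, 0.740).
- ED50 = 1.5: mean 0.8821, deviations (-0.2160, 0.1002, 0.1159), length 0.265, contrast (-0.816, 0.378, 0.438).
- Correlation of the two: 0.669 x 0.816 - 0.070 x 0.378 + 0.740 x 0.438 = 0.84.
- Correlation of the 1.5 mg contrast with the EMax contrast (-0.794, 0.230, 0.563): 0.98.

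**Step 4: critical values** (simulated, three candidates). About 2.24 with the protocol's set and 2.27 with the SAP's.

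**Step 5: effect on the overall test when the ED50 = 10 curve is true.**

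| Effect at 20 mg/kg (assumed) | Protocol's set | SAP's set | Difference (points) |
|---|---|---|---|
| 0.60 SD | 50.7% | 48.9% | 1.8 |
| 0.68 SD | 61.3% | 59.4% | 1.9 |
| 0.80 SD | 75.3% | 73.5% | 1.8 |

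The two tests reach different verdicts in between 2% and 3% of trials.

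**Step 6: effect on the sigmoid contrast alone.** At 0.68 SD the noncentrality of the 10 mg contrast is 5 x 0.68 x (0.582/0.8407) = 2.35; that of the 1.5 mg contrast is 0.84 x 2.35, about 1.98. Against 2.24 and 2.27 the chances of significance are 55% and 39%. Over 0.60 to 0.80 SD they run from 44% to 70% and from 31% to 53%. These describe one component of the maximum; the other candidates usually carry the test when it fails, which is why Step 5 shows only about 2 points.

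**The case against.** **The effect is small and the analysis is secondary.** This stands. Overall power moves by about 2 points, type I error is held under either set, and the primary hierarchical tests do not use these curves. Both documents also say that parameters will be estimated for all models, so the guessed ED50 governs the test and not the fitted curves.

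**The SAP was written for Amendment 5, so a comparison with Amendment 6 is unfair.** This does not rescue the value. The amendment log, used here only for version history, shows that the analysis-section list before Amendment 6 held EMax and Exponential alone, and that Amendment 6 added the sigmoid at 10 mg. A sigmoid at 1.5 mg matches neither version. Because of the version gap, the entry in SAP section 9 is only secondary evidence; the contradiction rests on SAP 8.5.2.2 against the protocol's synopsis and 11.3.1.

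**The protocol is not uniform either.** This stands in part. Its sample-size lists, which SAP 5 repeats, name two candidates, and its analysis sections name three. Wherever the protocol gives the sigmoid an ED50, however, it is 10 mg.

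**The power table cannot prove which candidate set produced it.** This is fair. The protocol's three-candidate set at 0.675 SD gives 13.7/72.6/60.7%, nearly as good a match. The wording of section 5 points to two candidates, and the sponsor's statistician can confirm it. Neither reading makes 60.7% the power for a 1.5 mg curve.

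**Conclusion.** The concern holds. SAP 8.5.2.2 and the protocol's analysis sections give different ED50 values, 1.5 and 10 mg, for the same candidate. This yields contrasts that correlate 0.84 and critical values of 2.27 and 2.24. The SAP's curve nearly duplicates EMax and leaves no intermediate shape in the set. The cost in overall power is about 2 points if the 10 mg curve is true, for assumed effects of 0.60 to 0.80 SD. The contrasts need no effect-size assumption; the powers do, because the planned effect is redacted and 0.68 SD was chosen to match the stated table. All figures read ED50 in mg/kg. The main harm is to pre-specification: two governing texts define two tests for the first secondary objective. It should be fixed, but it does not threaten the primary analysis.

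**What to change.** - In SAP 8.5.2.2, change the ED50 of the Sigmoid EMax candidate from 1.5 to 10 mg, keeping h = 2.4, to match the protocol synopsis and 11.3.1. Write both ED50 values in the unit used for the doses.
- If 1.5 mg was intended, say so in SAP section 9 as a change from the protocol, with the reason.
- In SAP 5, say which candidate set the power table refers to. Once the statistician confirms it, a sentence such as this would do: *The powers shown are for the two-candidate test (EMax, Exponential); section 8.5.2.2 adds Sigmoid EMax (ED50 = 10 mg, h = 2.4) as a third candidate.* The sample-size text in the protocol synopsis and 11.1 needs the same clarification when next amended.
- Update the protocol version cited in SAP section 1 if the SAP is meant to implement Amendment 6.

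The cost is a few lines of wording before the blind is broken. No new data are needed and the primary analysis does not change.

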11.1. Sample Size Determination

The number of participants is based on power considerations for the trabecular vBMD derived from HRpQCT at Month 12. The primary analysis method for this endpoint will be on the change from baseline within each treatment group, so the primary hypothesis to be tested is

$$H_0: \mu_T \leq 0 \text{ vs. } H_1: \mu_T > 0$$

where μ_T denotes the change from baseline for each dose of Setrusumab. Under the assumptions of a maximum change from baseline of [REDACTED], a standard deviation at both timepoints of [REDACTED] and a correlation between both measurements of [REDACTED], a sample size of 25 patients per group yields approximately 80% power for a one-sided test with significance level 0.025, if the data are analysed on the log scale using a t-test.

For a change from baseline of [REDACTED], with standard deviation as above the one-sided test would have a probability of 80% to yield a p-value below 5%, being considered indicative of a trend.

Following a review of the trabecular vBMD (radius) derived from HRpQCT at Month 6 of those subjects within the 20 mg/kg Setrusumab open label treatment group, a change from baseline standard deviation of [REDACTED] was observed. This yields to a correlation between baseline and Month 6 visits of [REDACTED] (much higher than the [REDACTED] that was originally assumed). If such a correlation is observed at Month 12, given 25 subjects per arm, the one-sided test would have a probability of 80% to yield a p-value below 5% for a change in baseline of [REDACTED].

As a secondary analysis, the MCPMod approach will be applied to the data in order to assess a non-flat dose-response curve and to obtain information about the underlying dose-response curve. Due to the missing placebo group, the power of this approach depends heavily on the underlying dose-response curve.

The following candidate models will be used:

- EMax (ED₅₀ of 1.5 mg)
- Exponential ($\delta = 2$)

Under the assumptions of each of the two candidate models being the true dose-response curve, and in addition an Sigmoid EMax model with parameters ED₅₀ = 10 mg and h = 2.4, a contrast test at a one-sided significance level of 2.5% has the following power for each of the three models:

Model	EMax	Exponential	Sigmoid EMax
Power	13.7%	73.2%	60.7%

The total sample size required is therefore determined as 100:

- 25 participants on open-label setrusumab (20 mg/kg)

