6 ANALYSIS POPULATIONS

Analyses for the primary efficacy endpoints and selected secondary endpoints will be analysed on the FAS, the Non-restricted FAS and the PP samples, while analyses for the remaining secondary efficacy endpoints will be analysed on the FAS sample only. Data collected for patients while taking placebo prior to protocol amendment 4.0 will not be included in any efficacy analysis (i.e. treatment comparisons), however will be included in efficacy descriptive statistic summaries.

Safety and tolerability endpoints will be analysed using the safety population. Data collected for patients while taking placebo prior to protocol amendment 4.0 will be included in all safety summaries.

Pharmacokinetic data will be analysed using the PK population.

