6.1 Full Analysis Set (FAS)

The Full Analysis set consists of all participants who are randomised to one of the blinded treatment arms and take at least 1 dose of study treatment. This does not include patients randomised to placebo prior to protocol amendment 4.0.

Participants will be analysed according to the randomised treatment.

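### The Sigmoid EMax candidate has two conflicting ED50 values (10 mg and 1.5 mg), and its required parameter estimates are not unique on three doses if all four parameters are free

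*SAP*

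**What the plan says.** - **Analysis text, protocol.** The synopsis (Efficacy Analysis) and section 11.3.1 list three MCP-Mod candidates: EMax (ED50 1.5 mg), Exponential (delta 2) and "Sigmoid EMax model with parameters ED50 = 10 mg and h = 2.4".
- **Analysis text, SAP.** Section 8.5.2.2 lists the same three names, but the third is "Sigmoid EMax (ED50 of 1.5 mg and h=2.4".
- **Sample-size text.** Protocol synopsis (Number of Participants), protocol 11.1 and SAP 5 list EMax and Exponential only. Power is then given "Under the assumptions of each of the two candidate models being the true dose-response curve" and, as the SAP puts it, "in addition an Sigmoid EMax model with parameters ED50 = 10 mg". The printed powers are 13.7% (EMax), 73.2% (Exponential) and 60.7% (Sigmoid EMax).
- **Output required.** SAP 8.5.2.2, protocol 11.3.1 and the synopsis ask for estimates from every model: "Parameter estimates and predicted values for each dose will be calculated for all models".
- **Data available.** The doses are 2, 8 and 20 mg/kg, and the open-label arm repeats 20 mg/kg. Of the FAS, SAP 6.1 says "This does not include patients randomised to placebo prior to protocol amendment 4.0". SAP 6 says that placebo-period data "will not be included in any efficacy analysis (i.e. treatment comparisons". The Non-restricted FAS (SAP 6.3) nominally contains placebo data, but the SAP 6 exclusion means it supplies no fourth dose level.
- **Declared changes.** SAP 9 reads "Not applicable". SAP 1 states that the SAP was written for protocol Amendment 5; the protocol supplied is Amendment 6.

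**The concern.** The dose-response relationship of Tr. vBMD is the first-listed secondary objective of a dose-finding study. Two statisticians, one following the SAP and one the protocol, would use different Sigmoid EMax contrasts on the same data.

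Both would also have to report Sigmoid EMax parameters without being told which are estimated. The model has four (E0, Emax, ED50, h) and there are three dose means. Left free, the reported ED50 and h would depend on software starting values or bounds rather than on the data. If either question is settled only after unblinding, the choice could be influenced by the results.

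**Working it through.** **Inputs.** Doses 2, 8, 20 mg/kg; 25 per arm; one-sided 2.5% (protocol 11.1, SAP 5). Residual df = 75 − 3 = 72. The documents print ED50 in mg while doses are in mg/kg; I take the printed values as mg/kg (assumption). The effect size, SD and correlation are redacted.

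**1. The printed power table.** I used the maximum of the contrast t statistics with a simulated critical value (about 2.22 for two candidates). Each curve is scaled to the same standardised effect at 20 mg/kg, taking E0 = 0 at dose 0. Solving for that effect from each printed figure with two candidates gives 0.678, 0.680 and 0.679, so one value, about 0.68, explains all three.

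Power (%) by true curve, at 0.679:

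| Candidate set | EMax | Exponential | Sigmoid, ED50 10 | Sigmoid, ED50 1.5 |
|---|---|---|---|---|
| Printed | 13.7 | 73.2 | 60.7 | – |
| EMax, Exponential | 13.7 | 73.1 | 60.8 | 11.4 |
| plus Sigmoid, ED50 10 | 13.9 | 73.3 | 61.5 | 11.5 |
| plus Sigmoid, ED50 1.5 | 13.9 | 71.6 | 59.5 | 11.9 |

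The 60.7% belongs to a true ED50 of 10. With a true ED50 of 1.5, the effect would have to be about 1.89 SD to reach 60.7% with two candidates. The first two computed rows are too close to separate (60.8 v 61.5). Replacing 10 by 1.5 in the three-candidate set costs 61.5 − 59.5 = 2.0 points.

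**2. The contrasts.** Shape g(d) = d^h / (ED50^h + d^h), h = 2.4. With equal n, the optimal contrast is g centred and scaled to length 1.

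- ED50 10: g = 0.0206, 0.3692, 0.8407; mean 0.4102; deviations −0.390, −0.041, 0.431; length 0.582; contrast (−0.67, −0.07, 0.74).
- ED50 1.5: g = 0.6661, 0.9823, 0.9980; mean 0.8821; deviations −0.216, 0.100, 0.116; length 0.265; contrast (−0.82, 0.38, 0.44).
- Correlation: 0.6693 × 0.8158 − 0.0703 × 0.3783 + 0.7397 × 0.4375 = 0.84.
- The EMax candidate's contrast is (−0.79, 0.23, 0.56). Its correlation with the ED50 1.5 version is 0.98, and with the ED50 10 version 0.93.

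**3. Identifiability.** For E0 + Emax·g(d) at three doses, the Jacobian in (E0, Emax, ED50, h) is 3 × 4 with rank 3, at ED50 10 and at 1.5. Fixing ED50 and h leaves two parameters with rank 2, and 3 − 2 = 1 df for lack of fit.

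To show the effect, take the planning means 0.021, 0.369, 0.841 (ED50 10, h 2.4; E0 = 0 and Emax = 1 assumed for scale). For a given h, ED50 solves (m20 − m8)/(m8 − m2) = 1.352; Emax and E0 then follow linearly. Each row below fits all three means exactly:

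| h | ED50 | Emax | Predicted at 5 mg/kg | Predicted at 14 mg/kg |
|---|---|---|---|---|
| 1 | 35.6 | 2.67 | 0.21 | 0.63 |
| 2 | 11.0 | 1.12 | 0.17 | 0.67 |
| 2.4 | 10.0 | 1.00 | 0.16 | 0.69 |
| 4 | 8.7 | 0.85 | 0.10 | 0.76 |
| 8 | 8.3 | 0.82 | 0.03 | 0.83 |

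The data cannot choose between these rows.

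**4. If ED50 and h are fixed, the value still matters.** Fitting the same means by least squares for E0 and Emax only, ED50 10 returns them exactly; ED50 1.5 returns 0.010, 0.596, 0.625.

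**The case against.** The strongest reply is that this is one slip and one missing sentence. In SAP 8.5.2.2, 1.5 mg is also the EMax value two lines above, so a copying error is plausible. The Amendment 6 analysis text consistently gives 10 mg, and the two-candidate wording in the sample-size sections may simply not have been updated. If ED50 and h were meant to be held fixed, the model is estimable. All of this is reasonable, but it is inference: no text says the values are fixed, and two values are printed. The SAP's basis on Amendment 5 does not explain the conflict either, since no protocol text supplied gives Sigmoid EMax an ED50 of 1.5 mg.

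A reader might infer three stronger things that the documents do not support.

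- **That predicted values at the studied doses are also undetermined.** They are not. Least-squares fitted values at 2, 8 and 20 mg/kg can be determined even when the parameters are not. Monotone means within the model's range are needed for an exact fit, not for unique fitted values. For means 0, 1, 0.5, for example, the best fit found was 0, 0.75, 0.75, reached with different ED50 and h.
- **That the power table proves a two-candidate set.** It cannot, given the redacted effect and the 60.8 v 61.5 comparison. The effect implied by the plan's 80% one-sample power is 0.584, which gives 11.2%, 59.7% and 48.4%, so the match depends on the back-solved 0.68.
- **That the primary result is at risk.** It is not: the hierarchical LSMeans tests do not use these models, and no decision rule uses an estimated ED50.

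**Conclusion.** The point holds, at minor severity. The documents conflict on whether Sigmoid EMax is a candidate and on its ED50, and the instruction to estimate parameters for every model is incomplete for this one.

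The size differs by consequence. The contrast changes materially in shape, and at 1.5 the third candidate nearly duplicates EMax. Power in the scenario behind the 60.7% changes by only about 2 points. The free parameter estimates, and predictions between doses, would be arbitrary.

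The contradiction is a matter of text and needs no assumption. The rank result needs only three distinct doses and four free parameters. The contrasts rest on reading mg as mg/kg. The power comparison rests on that reading, the common scaling at 20 mg/kg and the back-solved effect of 0.68.

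**What to change.** 1. Before unblinding, reconcile the candidate set and the Sigmoid EMax ED50 across the protocol synopsis (both places), protocol 11.1 and 11.3.1, and SAP 5 and 8.5.2.2. The value behind the printed 60.7% is 10 mg. Give the unit on the same scale as the doses, say which candidate set the power table refers to, and record any remaining difference from the protocol in SAP 9.
2. In SAP 8.5.2.2, protocol 11.3.1 and the synopsis, do not report freely estimated Sigmoid EMax parameters. Either use the model for the contrast step only and exempt it from the estimation sentence, or state that the listed ED50 and h are held fixed and only E0 and Emax are estimated.

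The cost is wording: no change to data, sample size or primary analysis. The drawback is that neither option gives an estimated ED50 or Hill slope for this model, and the second makes its fit conditional on the two fixed values.
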